### 7.7.6 Physical Examination

Clinically significant abnormalities identified from physical examination are recorded in the eCRF as Medical History, Sign and Symptom or Adverse Events as appropriate and will be listed and summarized as such (See Sections 7.4.1 [Medical History], 7.4.3 [Signs and Symptoms] and 7.7.2 [Adverse Events]).

Physical examination results (normal/abnormal) and details of abnormalities will be listed for each patient.

### 7.7.7 Other Safety Variables

The number and percentage of patients per Barthel index category will be tabulated by visit, treatment group and overall plitidepsin for the As Treated population.

Subgroup analysis of TEAE and clinically relevant laboratory tests will be performed by treatment group and overall plitidepsin based on the following prognostic factors of medical interest for the As Treated population:

- Sex: female or male
- Age at study entry: '18 to 39', '40 to 64' or ' $\geq$ 65 years'
- Race: Asian, black, white, or other
- Ethnic group: 'Hispanic or Latino' or 'Not Hispanic or Latino'
- Site location: each study site with more than 1/6 out of the randomised patients (ie, >33 randomised patients for the futility analysis and >101 randomised patients for the final analysis) will be considered as a group and the remaining study sites, ie, those study sites with less than 1/6 out of the randomised patients will be pooled together as a one single group.
- Previous COVID-19 vaccination status: 'Fully vaccinated', 'Non-fully vaccinated' or 'No vaccinated'
- SARS-CoV-2 viral load (log10 copies/mL) at Day 1 before study drug administration: `< 4', [4-7] or `> 7'

- Time between onset date of COVID-19 symptoms and initiation of study treatment: `≤ 5 days', `6 10 days' or `> 10 days'
- Charlson Comorbidity index (as derived using the eCRF data): '0 1' or '> 1'
- Geographical Region: Europe or Rest of the World
- Body mass index (kg/m^2) at Screening: '< 30' or ' $\geq$  30'
- Diabetes mellitus at Screening: 'None or diet controlled', 'Uncomplicated' or 'End-organ damage'
- Hypertension at Screening (defined as Hypertension [SMQ] in the Medical History form): Yes or No

Clinically significant chest abnormalities detected by chest examinations (computed tomography scan or x-ray) are recorded in the eCRF as Medical History, Sign and Symptom or Adverse Events as appropriate and will be listed and summarized as such (See Sections 7.4.1 [Medical History], 7.4.3 [Signs and Symptoms] and 7.7.2 [Adverse Events]).

Chest imaging results (normal/abnormal) and details of abnormalities will be listed for each patient.

# 7.8 Futility Analysis

The study may be terminated based on the conduct of a formal interim analysis of futility. Enrollment will not be temporarily halted while data for the interim analysis is being reviewed. In the case that the statistical stopping rule for futility is not met, the study will continue through planned completion. The interim analysis is planned as follows.

- A futility analysis of the primary efficacy endpoint will be performed when 33% of events (sustained withdrawal of supplementary oxygen) have been reached. This analysis will occur when the first 175 events have reached a sustained withdrawal of oxygen supplementation (in days) with no subsequent reutilisation during remaining study period.
- The rho family of beta-spending functions (with  $\rho$ =1.18) will be used for the calculation of the stopping boundaries for futility in order to control type II error, the stopping boundaries for the futility analysis will be calculated with the actual number of patients available in the ITT population at that moment; if the number of events at the futility analysis is 116 in a pair comparison, the beta spending corrected p-value to reject the alternative hypothesis should be higher or equal than 0.4199 and this p-value is associated with a hazard ratio  $\leq$  1.0382. The conditional power at this moment will be also calculated.

- If the recommendation of the IDMC was to discontinue one of the plitidepsin dosing arms at this futility analysis following the stopping rules, the study will continue from that point on a 1:1 randomisation fashion until the completion of the remaining treatment arms (203 patients per arm and 353 events of sustained withdrawal of supplementary oxygen in total necessary to perform the final analysis). The patients still ongoing in the dropped arm would continue to be followed-up as per protocol and a Bonferroni-adjusted type I error rate of 1.25% will be kept for the comparison of the primary endpoint between the remaining plitidepsin arm and the control arm.
- After submission of protocol amendment v7, some regulatory agencies has requested the analysis of prior primary efficacy endpoint data based on protocol amendment v6. Consequently, at the futility analysis time, an exploratory analysis with the patients fulfilling the prior requirements will be performed.

For the subset of patients with a pre-baseline (ie, in the prior month) Barthel Index  $\geq$  90, the percentage of patients who achieve complete recovery by Day 8 will be presented by treatment group and Clopper– Pearson 95% CI will be computed for the binomial proportion. In addition, the difference in the percentage of patients who achieve complete recovery by Day 8 between each dose of plitidepsin versus control arm will be presented for each dose of plitidepsin and the exact 95% CI will be computed for the difference in the percentage.

Complete recovery by Day 8 will be defined as

- i. meeting categories 0 to 2 on the 11-point WHO Clinical Progression Scale [at date of discharge when discharge is before or on Day 8 visit, or after the date of discharge but before or on Day 8 visit],
- ii. having Barthel index > 90/100 at time of discharge [when discharge is before or on Day 8 visit], and
- iii. with no readmission [or death] due to COVID-19 related signs or symptoms through Day 31

If discharge is after Day 8 visit then the patient will be considered as No complete recovery by Day 8.

If the 11-point WHO Clinical Progression Scale is missing or patient doesn't meet categories 0 to 2 between the date of discharge when discharge is before or on Day 8 visit and the Day 8 visit then the patient will be considered as **No complete recovery by Day 8**.

CONFIDENTIAL

If Barthel index at time of discharge is missing or  $\leq 90/100$  at time of discharge when discharge is before or on Day 8 visit then the patient will be considered as **No complete recovery by Day 8**.

If the 11-point WHO Clinical Progression Scale is between 0 and 2 and Barthel index is > 90 at time of discharge when discharge is before or on Day 8 however patient discontinues the study before Day 31, except due to death for any other reason than COVID-19 disease, then the patient will be considered as **No complete recovery by Day 8**.

The complete recovery by Day 8 rate between each dose of plitidepsin versus control arm will be analysed using a stratified logistic regression model. The model will be adjusted for the randomisation stratification factors, ie, Geographical Region (Europe vs. Rest of the World) and Charlson Comorbidity index (0-1 vs. >1) as derived using the eCRF data. The odds ratios, 95% CIs, and 2-sided p-values for the comparison of each dose of plitidepsin versus control arm will be presented.

The 2-sided p-values will be adjusted for multiplicity using the Hochberg step-up procedure to preserve the type 1 error rate in the comparison of each dose of plitidepsin versus control arm. The Hochberg step-up procedure will be implemented as following:

- Let  $p_1 \le p_2$  denote the ordered unadjusted 2-sided p-values with associated null hypotheses  $H_{01}$  and  $H_{02}$ , where  $H_{0i}$  = complete recovery by Day 8 rate in plitidepsin [1.5 mg or 2.5 mg] arm = complete recovery by Day 8 rate in control arm.
- Then we follow the next stepwise procedure:
  - If  $p_2 \leq 0.05$ , reject  $H_{01}$  and  $H_{02}$  stop; else continue
  - If  $p_1 \leq 0.05/2$ , reject  $H_{01}$  and stop
- Adjusted 2-sided p-values will be calculated as:
  - $\circ \quad q_2 = p_2$
  - $\circ q_1 = \min[2^* p_1, q_2]$

The adjusted 2-sided p-values for multiplicity using the Hochberg step-up procedure will be also presented.

The primary efficacy analysis described above will be performed using the FAS population.

 To maintain continuous study integrity, analysis will be conducted by an independent team. The Tables, Figures and Listings required for the interim analysis will be created in a separate and restricted-access study area. The conditional power (probability) that the final study result will be statistically significant, given the data observed thus far and assuming the original Sponsor Name: Pharma Mar S.A. Sponsor Protocol ID: APL-D-003-20

design effects for the remainder of the study will be calculated by the unblinded independent statistician or delegate and sent to the IDMC at the time of the interim analysis. The IDMC will consider the option of declaring futility based on the crossing of the futility boundary as well as conditional power. Details of the process for the interim analysis and the resulting controlled dissemination of interim analysis data will be detailed in the IDMC Charter document.

In addition, at the time when 30 patients have been treated per group with a 30 day follow-up, the IDMC Support Team will provide the IDMC Chairperson with unblinded information on the number of deaths and SAEs. Upon review of this data, if either the difference in the percentage of deaths or SAEs Grade  $\geq$ 3 is at least 20% higher in any plitidepsin arm in comparison with the control arm, IDMC Chairperson will contact the other members of the IDMC and the clinical trial would be halted for a specific safety analysis by the IDMC if she/he deems it necessary.

The IDMC can ask for a temporary halt of the clinical trial at any time to better analyse any potential benefit/risk concern.

In addition to the above analysis, meetings for an IDMC data review may be scheduled to ensure proper safety assessment during enrollment and study conduct. Initially, proposed timelines for meeting frequency to review unblinded safety data will be as follows: the IDMC will develop a charter and establish criteria for when meetings are to occur, plus identify a time for the planned interim analysis of futility should this latter event fall outside the times of the reoccurring meetings. The IDMC review meetings will occur until database lock or at an earlier time deemed suitable by the IDMC. This meeting schedule may be modified based on the observed patient accrual rates or signals seen in the safety data.

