## 2.2 Overall Study Design

This is a randomised, multicentre, open-label, controlled Phase 3 study in which adults requiring hospital admission and oxygen supplementation for management of moderate COVID-19 infection will be randomised in 1:1:1 to:

- Plitidepsin 1.5 mg arm: Patients will receive plitidepsin 1.5 mg/day intravenous (IV) in addition to dexamethasone on days 1 to 3;
- Plitidepsin 2.5 mg arm: Patients will receive plitidepsin 2.5 mg/day IV in addition to dexamethasone on days 1 to 3;
- Control arm: Patients will receive dexamethasone IV on Days 1 to 3. Additionally, in accordance with local treatment guidelines, patients in this group may receive a regulatory-approved antiviral treatment.

The study allows up to a total cumulative dose of 60 mg of dexamethasone base (calculation of the total dose will also include corticosteroids administered within 72 hours before the start of the study treatment and dexamethasone administered as premedication).

Randomisation will be stratified for 3 factors:

- Geographical region (Europe vs. Rest of the World);
- Charlson Comorbidity Index (0-1 vs. >1); and
- Barthel Index (≥90 versus <90)

From treatment initiation on Day 1, patients will be followed in the hospital for at least 4 days and then through Day 31 ( $\pm$ 3 days) or resolution/stabilisation of treatment-related adverse events (AEs), treatment-emergent adverse events (TEAEs) of special interest, and serious adverse events (SAEs). Patients discharged from the hospital prior to Day 8 will return to an out-patient clinic for assessments on Days 8 ( $\pm$ 1 day), and 31 ( $\pm$ 3 days). On Day 15 ( $\pm$ 1 day), patients will be followed up in remote or on-site visit (Appendix 4).

An independent Data Monitoring Committee (IDMC) will oversee study conduct (safety and primary endpoint), including analysis of summary safety data as per the trial requirements.

The study is expected to randomise approximately 609 patients (203 in each arm) over a period of 20 months.

Patients will be considered to be on study from the signature of the informed consent form until the end of the follow-up period, that is, completion of the protocol-specified follow-up visit on Day 31 ( $\pm$ 3 days) or until resolution/ stabilisation of treatment-related AEs, TEAEs of special interest, and SAEs that occurred through Day 31, whichever is longer.

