# 8. Changes in Planned Analysis

Despite wording in Protocol that WHO score 0 requires a test with RNA undetected (which would be achieved with a PCR or similar test), as scarce cases have been reported, Pharma Mar is accepting negative antigen tests (which is a protein detection test, and not RNA detection test) qualifying for score of 0.

Recruitment was stopped due to slow recruitment before reaching the 33% of events by Pharma Mar decision and futility analysis was cancelled.

An exploratory analysis of the comparison of the primary efficacy endpoint between each dose of plitidepsin versus control arm receiving and not receiving the antiviral control arm, ie, the regulatory-approved antiviral for those patients randomised to the control arm (remdesivir or favipiravir), will be performed.

CONFIDENTIAL

An exploratory analysis of the prior primary efficacy endpoint based on protocol amendment v6 will be performed at the final analysis time due to some regulatory agencies request.

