#### Table 14.2.1.4 Complete Recovery by Day 8 as Defined in Protocol Amendment Version 6 (Full Analysis Set)\*

Variable	Plitidepsin 2.5mg	Plitidepsin 1.5mg	Control Arm
	(N=XXX)	(N=XXX)	(N=XXX)
Patients with a pre-baseline Barthel Index $\ge 90$	XXX	XXX	XXX
Complete Recovery by Day 8, n (%)	xxx (xx.x)	xxx (xx.x)	xxx (xx.x)
95% CI for Complete Recovery by Day 8 (%) [a]	xx.x – xx.x	xx.x - xx.x	xx.x – xx.x
Non Complete Recovery by Day 8, n (%)	xxx (xx.x)	xxx (xx.x)	xxx (xx.x)
Difference of Complete Recovery by Day 8 (%) [b]	XX.X	XX.X	
95% CI for Difference of Complete Recovery by Day 8 (%) [c]	XX.X – XX.X	XX.X – XX.X	
Adjusted Odds Ratio [d,e]	X.XXX	X.XXX	
95% CI for Adjusted Odds Ratio [d,e]	X.XXX - X.XXX	X.XXX - X.XXX	
2-sided p-value [d]	X.XXX	X.XXX	
2-sided p-value adjusted for multiplicity [d,f]	X.XXX	X.XXX	

N = number of patients in analysis set; n = number of patients in each category. % = percentages are calculated based on the number of patients with a pre-baseline Barthel Index  $\geq 90$  as the denominator.

CI = Confidence interval.

Notes: Complete recovery by Day 8 is defined as

- i. meeting categories 0 to 2 on the 11-point WHO Clinical Progression Scale [at date of discharge when discharge is before or on D8 visit, or after the date of discharge but before or on D8 visit],
- ii. having Barthel Index > 90/100 at time of discharge [when discharge is before or on Day 8 visit], and
- iii. with no readmission [or death] due to COVID-19 related signs or symptoms through Day 31

[a] Clopper-Pearson 95% confidence interval.

[b] Difference of Complete Recovery by Day 8 = Complete Recovery by Day 8 for the plitidepsin arm - Complete Recovery by Day 8 for control arm.

[c] Exact 95% confidence interval.

[d] Adjusted Odds Ratio, 95% CI and 2-sided p-values based on a stratified logistic regression model with fixed effects of treatment group and randomisation stratification factors, ie, geographical region (Europe vs. Rest of the World) and Charlson Comorbidity Index (0-1 vs. >1) as derived using the eCRF data as covariates.

[e] Statistics calculated relative to Control Arm

[f] P-values adjusted for multiplicity using the Hochberg step-up procedure.

\* Exploratory analysis of the prior primary efficacy endpoint based on protocol amendment v6 due to some regulatory agencies request. Reference: Listing 16.2.6.1 and 16.2.6.2

- Table template TEF009A.
- This Table will be created only at the the time of the Futility Analysis.

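### The exploratory v6 recovery analysis admits a pre-illness Barthel of 90 but scores a return to 90 as failure, and its shell note ties the table to the cancelled futility analysis

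*SAP*

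**What the plan says.** **Who is analysed.** Section 7.8 opens the v6 analysis with "For the subset of patients with a pre-baseline (ie, in the prior month) Barthel Index" of 90 or more. The footnote to Table 14.2.1.4 uses the same denominator: "percentages are calculated based on the number of patients with a pre-baseline Barthel Index" at or above 90.

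**What counts as recovery.** The functional criterion in Section 7.8 is "having Barthel index > 90/100 at time of discharge", and the shell repeats it as "having Barthel Index > 90/100 at time of discharge". Section 7.8 also gives an explicit failure rule, which begins "If Barthel index at time of discharge is missing or" and goes on to cover values of 90 or below. Its rule for patients who leave the study before Day 31 again uses a score above 90.

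**When it is produced.** Section 7.8 places the analysis at the futility look. Section 8 records that recruitment stopped before the trigger was reached and that the futility analysis was cancelled. It then states: "An exploratory analysis of the prior primary efficacy endpoint based on protocol amendment v6 will be performed at the final analysis time", because some agencies asked for it. The programming note under Table 14.2.1.4 reads: "This Table will be created only at the the time of the Futility Analysis". The SAP text and the shells are both version 4.0, dated 21 April 2023, and the later addendum does not list this table.

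**The concern.** A reader of a table headed complete recovery will assume that a patient who leaves hospital as able as before the illness can count as recovered. For patients at exactly 90 that is not so: they must leave at 95 or 100, at least 5 points better than before COVID-19. The definition says nothing about this group, and the table does not show its size.

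At stake is how agencies read an analysis that they requested. The recovery rate is somewhat too low as a measure of return to pre-illness function, and the between-arm difference is slightly compressed.

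The timing conflict is a separate matter. Two current version 4.0 texts give opposite instructions for the same output, and a programmer working only from the shell would leave it out of the final package.

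**Working it through.** The SAP gives no rate, power or sample size for the v6 endpoint, so there is no figure to reproduce. The check is logical, followed by an illustration on assumed values.

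**Step 1: reachable scores.** Every item score in SAP Appendix 3 is a multiple of 5. Taking 0 as the score for an item not achieved, totals run from 0 to 100 in steps of 5. Table 14.3.7.1 has its own 90% row.

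**Step 2: apply both rules to a patient whose discharge score equals the pre-baseline score.**

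| Pre-baseline and discharge | Admitted (90 or more) | Meets Barthel criterion (above 90) |
|---|---|---|
| 85 | no | not applicable |
| 90 | yes | **no** |
| 95 | yes | yes |
| 100 | yes | yes |

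The rules part at one score, 90.

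**Step 3: does anything else in the plan correct for it?** Randomisation separates 90 or more from below 90 (Section 2.2), so it does not balance 90 against 95 and 100. The logistic model for this endpoint adjusts for region and Charlson index only.

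**Step 4: possible size.** Let f be the share of the subset at exactly 90; the SAP does not give it. Assume that nobody exceeds the pre-illness score and that recovery does not otherwise depend on that score.

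- Highest reachable rate = 1 − f
- Understatement at an assumed 30% recovery rate = f × 30%
- Observed difference when the true difference is an assumed 15 points = (1 − f) × 15

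| f | Highest rate | Understatement (points) | 15-point difference becomes |
|---|---|---|---|
| 2% | 98% | 0.6 | 14.7 |
| 5% | 95% | 1.5 | 14.25 |
| 10% | 90% | 3.0 | 13.5 |
| 20% | 80% | 6.0 | 12.0 |

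**Step 5: chance imbalance.** The actual arm size is not stated. The site-location rule in Section 7.6.4 equates one sixth of patients at futility with 33, that is 6 × 33 = 198 in total and 198 / 3 = 66 per arm, and recruitment stopped before that event count. Taking 60 per arm as an assumption, three extra patients at 90 in one arm shift the difference by at most 3 / 60 = 5 points, if all three would otherwise have recovered. At 30% the expected shift is 5 × 0.30 = 1.5 points.

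**Step 6: test the remedy.** Let B be the pre-baseline and D the discharge score. Accepting D above 90 or D at least B adds only the pair B = 90, D = 90, because for B of 95 or 100 any D at or above B already exceeds 90. Lowering the cut to D of 90 or more would also add B = 95, D = 90 and B = 100, D = 90, which are losses of function.

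**The case against.** The strongest reply is that entry and success thresholds need not match. The rule is absolute, fully computable and stated consistently, which reads as deliberate. The table is titled as the protocol v6 definition, agencies asked for that endpoint, and protocol v6 is not shown. Reproducing a legacy endpoint faithfully is not a mistake. This stands: the v6 result should remain as defined, and the mismatch is a limit on interpretation rather than a proven error.

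A reader might infer that the rule biases the comparison. The documents do not support that. It is identical in all arms, and a chance imbalance at 90 is ordinary sampling variation that the confidence interval covers. The 5-point shift in Step 5 is a worst case.

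A reader might also infer that the requested output will never be made. Section 8 orders it at the final analysis, the shells describe themselves as guidance, and the retained shell carries a footnote on the agency request. The note is a leftover that conflicts with Section 8; it does not override it.

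Some of the information is available elsewhere. Table 14.3.7.1 shows pre-illness Barthel by arm with 90 as a category, though for the As Treated population, and Listing 16.2.6.2 gives each patient's scores. Neither gives the count in the analysed subset beside the result.

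**Conclusion.** The point holds and is minor. On the SAP's own rules, patients admitted at a Barthel of exactly 90 who return to 90 are non-responders. This lowers recovery rates in every arm and slightly dilutes differences. The SAP does not allow the amount to be quantified: the 0.6 to 3.0 points for 2% to 10% at 90 rest on an assumed 30% recovery rate and on nobody exceeding the pre-illness score. The analysis is exploratory and has no bearing on the v7 primary endpoint or its error control.

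The programming note contradicts Section 8 outright. That part needs no assumption.

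**What to change.** 1. Delete the programming note under Table 14.2.1.4, or replace it with an instruction to produce the table at the final analysis, in line with Section 8.
2. Keep the v6 definition as the labelled result, and state that its cut-offs are retained as written.
3. Add one supportive row or table, labelled post hoc because the database was locked on 26 April 2023, in which criterion ii becomes: discharge Barthel above 90, or at least the patient's own pre-baseline value. A missing discharge score stays a failure and the other criteria are unchanged. Do not simply lower the cut to 90, since that would count a fall from 100 to 90 as complete recovery.
4. Footnote the number of patients per arm in the analysed subset with a pre-baseline Barthel of exactly 90.

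The cost is one edited note, one derived flag, one extra row or table and one footnote, all from data already collected. The drawback is a second version of an exploratory endpoint, which the post hoc label keeps in its place.
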